6.1 Efficacy Evaluable Analysis Set

The analysis of objective response will be conducted on the Efficacy Evaluable Analysis set defined as all subjects that are enrolled to a dose expansion cohort and receive at least 1 dose of AMG 994 or AMG 404 with at least 1 tumor lesion that is measurable in contrast-enhanced CT as defined by modified RECIST 1.1, with the following exceptions.

The following subjects will be excluded from the Efficacy Evaluable Analysis set:

- 1) Subjects who are lost to follow up and have no on study radiological assessments and
- 2) Subjects who have been on study less than 8 weeks and have no on study radiological assessments.

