### **7.2.2 Reasons for Removal From Study**

Reasons for removal of a subject from the study are:

- Decision by sponsor
- Withdrawal of consent from study
- Death
- Lost to follow-up

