### **9.3 Analysis Sets, [REDACTED] and Covariates**

#### **9.3.1 Analysis Sets**

The analysis of all endpoints, unless noted otherwise, will be conducted on the Safety Analysis Set defined as all subjects that are enrolled and receive at least 1 dose of AMG 994 or AMG 404.

[figure not shown]
The analysis of DLT in the initial safety review period [REDACTED] will be conducted on the Early DLT Analysis set defined as all subjects that are enrolled and receive at least 1 dose of AMG 994 with an evaluable early DLT endpoint (evaluable in AMG 994 monotherapy cohort per [Table 6-2](#)).

The analysis of DLT in the cumulative safety review period will be conducted on the Cumulative DLT Analysis set defined as all subjects that are enrolled and receive at least 1 dose of AMG 994 or AMG 404 with an evaluable cumulative DLT endpoint (experience a DLT during monotherapy cohort or evaluable in combination therapy cohort per [Table 6-2](#)).

The analysis of objective response will be conducted on the Efficacy Evaluable Analysis set defined as all subjects that are enrolled to a dose expansion cohort and receive at least 1 dose of AMG 994 or AMG 404 with at least 1 tumor lesion that is measurable in contrast-enhanced CT as defined by modified RECIST 1.1, with the following exceptions. The following subjects will be excluded from the Efficacy Evaluable Analysis set: 1) subjects who are lost to follow-up and have no on study radiological assessments and 2) subjects who have been on study less than 8 weeks and have no on study radiological assessments.

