4.1 Planned Covariates

The relationship of covariates if applicable, to efficacy endpoints will be explored as appropriate.

5. Definitions

Adverse Event (AE)

An adverse event is any untoward medical occurrence in a clinical study subject irrespective of a causal relationship with the study treatment.

Age at Enrollment

Subject age at enrollment will be determined using the age in years reported in the clinical database.

Area under the Curve (AUC)

Area under the plasma concentration-time curve reflects the actual body exposure to drug after administration of a dose of the drug.

Baseline

For any variable, unless otherwise specified the baseline is the last non-missing assessment taken prior to the first administration of AMG 994 and for cohorts with concurrent administration of AMG 994 and AMG 404 first administration of AMG 994 and AMG 404. Where baseline measurements are taken on the same day as the study specified treatment and no times are present, it will be assumed that these measurements are taken prior to the study specified treatment being administered.

Baseline ECG Values in Triplicate

The mean of the triplicate ECG results should be calculated for Baseline. For all post-baseline ECG, the mean of triplicate ECG results at the same assessment will be calculated and used in the analysis. When an ECG is missing within a triplicate, all available data will be averaged for that time point.

Best Overall Response (BOR)

The best overall response is the best response recorded from the start of the study treatment until the end of treatment or disease progression/recurrence (taking as reference for PD the smallest measurements recorded since the treatment started). Overall response assessments occurring after the start of the first subsequent anticancer therapy will not be included.

In general, the subject's best response assignment will depend on the findings of both target and non-target disease and will also take into consideration the appearance of new lesions.

BOR for a subject is the best observed disease response per modified RECIST 1.1 in the following order: Complete response (CR), Partial response (PR), Stable disease (SD), Progressive disease (PD) and Not evaluable (NE). A best overall response of CR and PR require confirmation by a repeat, consecutive scan at least 4 weeks after the first documentation of response.

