It is defined as when the last subject is assessed or receives an intervention for the purposes of final collection of data for the primary endpoint(s), whether the study was conducted as planned in the protocol or was terminated early.

End of Treatment (EOT)

Defined as the last assessment for the protocol-specified treatment of the study for an individual subject.

Enrollment

A subject is considered enrolled when the investigator decides that the subject has met all eligibility criteria.

Fridericia-corrected QT Interval (QTcF)

The Fridericia correction will be calculated from the investigator reported QT (msec) and RR interval (msec), as follows:

$$QTcF=QT/(RR/1000)^{1/3}$$

Investigational Product

The term 'Investigational product' is used in reference to AMG 994 and combination of AMG994 and AMG 404.

Last IP Dose Date

The last IP dose date for each subject is defined as the latest date IP administered.

Objective Response Rate (ORR)

Objective response rate is defined as the proportion of patients with a Best Overall Response (BOR) of confirmed CR or PR.

Overall Survival (OS)

Overall survival (OS) is defined as the time from the start of treatment until event of death due to any cause. Subjects still alive will be censored at the date last known to be alive. If the date last known to be alive is after the date that triggers the analysis (i.e., the data cutoff date), the subject will be censored at the analysis trigger date.

For subjects not known to have died, their last date known to be alive will be determined as the latest date associated with clinic visits before data cutoff date including, for example, but not limited to the following:

[figure not shown]
- Survival status: Last contact date if status of subject is "Alive"
- End of study date if the subject's primary reason for ending study is not "Lost to follow-up"
- Any subsequent anti-tumor therapy initialization date
- AE start or end date
- Procedure and concomitant medication start/end date
- Date of lesions assessments
- Visit date of vital signs; physical exam; ECOG; sample collection for labs
- Date of last investigational product administration

Progression Free Survival (PFS)

The PFS is defined as interval from the start of treatment to disease progression or death due to any cause (whichever comes first).

PFS (in months) = (Earliest date of disease progression, death, censor – Date of first dose + 1)/30.4

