7.2 Primary Analysis

The primary analysis will occur when target enrollment is complete and each subject either completes 6 months on study or withdraws from the study.

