9.1 General Considerations

Unless otherwise specific, all described analyses will be conducted on the Safety Analysis Set. Descriptive statistics will be provided for selected demographics, safety, PK, PD, and biomarker data by dose, dose schedule, and time as appropriate.

Descriptive statistics on continuous data will include means, medians, standard deviations, and ranges, while categorical data will be summarized using frequency counts and percentages. Graphical summaries of the data may also be presented.

Confidence intervals (CI) for proportions will be estimated using an exact method proposed by Clopper-Pearson ([Clopper & Pearson, 1934](#)). Kaplan-Meier methods will be used to estimate the median and percentiles for time to event endpoints with CI calculated using the Brookmeyer and Crowley method ([Brookmeyer & Crowley, 1982](#)). Kaplan-Meier methods will be used to estimate landmarks for time to event endpoints (e.g., 1-year OS) with the Greenwood formula ([Kalbfleisch & Prentice, 1980](#)) used to estimate the standard error used in CI calculation

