9.5.2 Analyses of Secondary Efficacy Endpoint(s)

Listings of secondary efficacy endpoints will be produced for all subjects in the dose-escalation cohorts and the dose-expansion cohorts.

For all subjects in the Efficacy Analysis Set, the proportion of subjects and 95% CL with an objective response (complete or partial response per modified RECIST 1.1) will be tabulated by tumor type and planned dose level and schedule.

For all subjects in the Efficacy Analysis Set, Kaplan-Meier methods will be used to estimate the time of event curve, median time to event, and percentiles with 95% CI for

1) Duration of response (DOR, per modified RECIST 1.1),

2) Overall survival (OS)

3) Progression-free survival (PFS, per modified RECIST 1.1)

4) Time to progression (TTP, per modified RECIST 1.1) and

5) Time to subsequent therapy.

Kaplan-Meier methods will be used to estimate appropriate landmarks for DOR, OS, PFS and TTP (eg, 1-year PFS)

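### Part 2 ORR is computed on a set that drops treated subjects with no on-study scan, which can only raise it or leave it unchanged; OS and PFS are placed on a set that is not defined

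*SAP*

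**What the plan says.** **Objective response.** SAP 6.1 and Protocol 9.3.1 define the Efficacy Evaluable set in the same way. It starts from dose-expansion subjects who received at least one dose and have a measurable lesion. It then removes two unscanned groups: those lost to follow-up, whatever their time on study, and "Subjects who have been on study less than 8 weeks and have no on study radiological assessments". SAP 5 states that "Objective response rate is defined as the proportion of patients with a Best Overall Response (BOR) of confirmed CR or PR", and requires a CR or PR to be confirmed on a repeat scan at least 4 weeks after the first. The primary analysis waits until "each subject either completes 6 months on study or withdraws from the study" (SAP 7.2). Neither document plans an ORR that keeps the removed subjects, even as a sensitivity analysis.

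**Time-to-event endpoints.** SAP 9.5.2 says: "For all subjects in the Efficacy Analysis Set, Kaplan-Meier methods will be used to estimate the time of event curve", and then lists DOR, OS, PFS, TTP and time to subsequent therapy. Protocol 9.4.2.2 does the same. No set of that name is defined in SAP section 6 or Protocol 9.3.1. SAP 6.1 ties the Efficacy Evaluable set to objective response only. SAP 9.1 sets a default, unless something else is specified, under which "all described analyses will be conducted on the Safety Analysis Set".

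**The concern.** An 8-week rule is reasonable at an early data cut, when some subjects are still waiting for their first scan. At the planned primary analysis that purpose has largely gone, because everyone has reached 6 months or has left. The rule then removes mainly people who left or died early. They are treated failures or unknowns, and removing them pushes ORR in one direction only. ORR by tumor type is the first-listed activity endpoint.

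For OS and PFS, two programmers could follow the same text and use different sets. Under one of the two choices, subjects who die before a first scan disappear from analyses in which death from any cause is an event.

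**Working it through.** **1. The plan's own figure.** SAP 3.2 takes 30 subjects and a 20% response rate, so r = 0.20 × 30 = 6. The Clopper-Pearson limits are the 2.5% quantile of Beta(r, n−r+1) and the 97.5% quantile of Beta(r+1, n−r). For 6/30 they are 7.7% and 38.6%, which round to the stated 8% and 39%.

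**2. Effect of the exclusions on ORR.** A confirmed response needs a first scan and a repeat scan. A subject with no on-study scan therefore cannot be a responder, and r does not change. If k of n treated subjects with measurable disease are dropped:

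reported ORR = r/(n−k) = (r/n) × n/(n−k), and n/(n−k) ≥ 1.

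Dropped subjects also shrink n for good, since Protocol 4.2.1 rules out replacement of subjects withdrawn or removed in Part 2. The documents give no rate of unscanned subjects, so k is assumed. All 30 are taken to have measurable disease.

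| k | ORR | exact 95% CI | factor n/(n−k) |
|---|---|---|---|
| 0 | 6/30 = 20.0% | 7.7 to 38.6 | 1.00 |
| 1 | 6/29 = 20.7% | 8.0 to 39.7 | 1.03 |
| 3 | 6/27 = 22.2% | 8.6 to 42.3 | 1.11 |
| 6 | 6/24 = 25.0% | 9.8 to 46.7 | 1.25 |

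**3. An uneven cut.** Take a subject with no scan who is not lost to follow-up. If that subject leaves in week 9, the subject stays in the denominator as a non-responder. If the same subject leaves in week 7, the subject is removed.

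**4. Futility rule.** Its table counts treated subjects. Stopping requires no responder in 10, or exactly one in the first 10 and none in the next 10:

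- True rate 5%: 0.95^10 + (10 × 0.05 × 0.95^9) × 0.95^10 = 0.599 + 0.315 × 0.599 = 78.7%.
- True rate 20%: 1 − (0.107 + 0.268 × 0.107) = 86.4% continue.

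Both match SAP 7.1. The rule as written is not touched by the exclusions.

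**5. OS, if the undefined set is the Efficacy Evaluable set.** Suppose a share p of subjects dies before a first scan, taken at time c, and all of them are dropped. For t > c, reported S(t) = S(t)/(1−p). With exponential survival and median m, p = 1 − exp(−ln2 × c/m), and the reported median is m + c. The first-scan day is blacked out and the rule reaches to 8 weeks, so c is shown at both 4 and 8 weeks (28/30.4 = 0.92 and 56/30.4 = 1.84 months). With m = 6 months, an assumption:

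- c = 4 weeks: p = 10.1%, reported median 6.9 months, 6-month OS 0.50/0.899 = 56%.
- c = 8 weeks: p = 19.2%, reported median 7.8 months, 6-month OS 0.50/0.808 = 62%.

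These figures show direction and sensitivity to c. They do not bound the bias.

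**The case against.** A response-evaluable denominator is common in phase 1, it is stated identically in both documents, and nothing is tested on it. Listings of efficacy endpoints cover all subjects (SAP 9.5.2), so a reader can recover the all-treated proportion. Few subjects should be unscanned: there is a cycle 1 scan and an end-of-treatment scan, imaging continues after stopping for reasons other than progression (Protocol 8.2.2), and Appendix 11 asks for imaging after symptomatic deterioration. Dropping one to three subjects moves ORR by 0.7 to 2.2 points, inside an interval about 31 points wide (38.6 − 7.7). All of this stands, and it limits the importance of the point. It does not change the direction.

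Three stronger readings are tempting and should not be made:

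- *A reader might infer that at the primary analysis the 8-week rule can catch only early leavers and deaths.* Protocol 4.4.1 provides for early termination, and Protocol 7.2.2 lists a sponsor decision among the reasons for removal. Either could leave subjects unscanned for reasons unrelated to disease. Counting them as non-responders would understate ORR.
- *A reader might infer that SAP 5 already classes these subjects as not evaluable, so that SAP 6.1 contradicts it.* The category exists, but no passage explicitly assigns it to a subject with no scan.
- *A reader might infer that the exclusions weaken the futility rule.* They do not, because that rule counts treated subjects.

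On the set name, the likeliest explanation is a slip for the Efficacy Evaluable set, since SAP 9.5.2 uses the same name for ORR. That makes the deletion of early deaths more likely, not less.

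**Conclusion.** The point holds for ORR. Relative to all treated Part 2 subjects with measurable disease, the two no-scan exclusions raise ORR or leave it unchanged, by the factor n/(n−k). In the SAP's example this is 20.0% to 20.7% for one subject dropped and 22.2% for three, with k assumed. It concerns a descriptive secondary estimate, is inexpensive to correct, and is not a design failure. The direction is established only for the no-scan exclusions. It should not be extended to the measurable-lesion restriction, because subjects with non-target disease only can be enrolled and can reach CR.

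For OS and PFS the point is conditional. The set is undefined. If it is the Efficacy Evaluable set, early deaths without a scan are deleted and both estimates are biased upward. A reader might take the 4-week figures above as a ceiling. The documents do not support that, because the scan day is blacked out, the rule reaches to 8 weeks, and the survival curve is assumed. A reader might also assume that every time-to-event endpoint is affected. No bias is shown for TTP, where death without progression is censored, or for time to subsequent therapy, where only new therapy is an event. DOR is computed only in confirmed responders, none of whom is removed.

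**What to change.** - **ORR:** make the primary denominator all treated Part 2 subjects with measurable disease at baseline. State that a subject with no post-baseline scan is classed as not evaluable and counts as a non-responder.
- **Sensitivity analysis:** keep the current Efficacy Evaluable set for this purpose, with the number of and reasons for exclusions by tumor type. Inclusion criterion 106 also admits evaluable-only disease, so report the number treated beside the ORR denominator.
- **Time-to-event endpoints:** replace the name Efficacy Analysis Set in SAP 9.5.2 and Protocol 9.4.2.2 with defined sets. Analyse OS and PFS on all treated Part 2 subjects. Put TTP and time to subsequent therapy on the same set for consistency only.

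The cost is wording in SAP 6.1 and 9.5.2, and in Protocol 9.3.1 and 9.4.2.2 at the next amendment, with no new data. The reported ORR may be slightly lower. It may also be understated where scans are missed for reasons unrelated to disease, for example after early study termination; the retained sensitivity analysis would show this.

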6.2 Safety Analysis Set

[figure not shown]
Safety Analysis Set defined as all subjects that are enrolled and receive at least 1 dose of AMG 994 or AMG 404.

6.3 Early DLT Evaluable Analysis Set

The analysis of DLT in the initial safety review period (through [REDACTED]) will be conducted on the Early DLT Analysis set defined as all subjects that are enrolled and receive at least 1 dose of AMG 994 with an evaluable early DLT endpoint (evaluable in AMG 994 monotherapy cohort per Table 6.4.1).

6.4 Cumulative DLT Evaluable Analysis Set

The analysis of DLT in the cumulative safety review period will be conducted on the Cumulative DLT Analysis set defined as all subjects that are enrolled and receive at least 1 dose of AMG 994 or AMG 404 with an evaluable cumulative DLT endpoint (experience a DLT during monotherapy cohort or evaluable in combination therapy cohort per Table 6.4.1).

[figure not shown]
7. Planned Analyses

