**Table 4-1: MSLN Expression in Solid Tumors**

Tumor Type	Patients with MSLN Expression – Positive Disease (%)
Mesothelioma	82
Epithelioid	95
Sarcomatoid	0
Pancreatic adenocarcinoma	85
Epithelial ovarian cancer	70
High-grade serous	75
Endometrioid	69
Mucinous	11
Clear cell	52
NSCLC	57
Adenocarcinoma	64
Squamous	21
SCLC	0
Esophageal cancer	28
Gastric cancer	47
Biliary cancer	
Extrahepatic	95
Intrahepatic	10
Other or unspecified	42
Colorectal cancer	30
Cervical cancer	25
Endometrial cancer	59
Breast cancer	
Triple negative	66
Other	1.6
Unspecified	9

MSLN = mesothelin, NSCLC = nonsmall-cell lung cancer

Study assessments will include measures of safety, tolerability, PK, and pharmacodynamics, immunogenicity, and preliminary anti-tumor activity.

AMG 994 will be administered by [REDACTED] cycle

(on days [REDACTED]) and AMG 404 will be administered by

[REDACTED] cycle. The study will be

conducted in 2 parts: Part 1 – Dose Exploration and Part 2 – Dose Expansion. Part 1 is aimed at evaluating the safety, tolerability, PK, and pharmacodynamics of AMG 994 and AMG 404 combination using sequential and concurrent initiation of dosing: (a) 1 cycle of AMG 994 monotherapy followed by combination of AMG 994 and AMG 404 from cycle 2 onwards and (b) AMG 994 and AMG 404 dosing starting on cycle 1 day 1. The MTD/MTCD of the combination in subjects with locally advanced or metastatic solid tumors will be determined using a Bayesian Logistics Regression Model (BLRM) design. Part 2 will further evaluate the safety of the MTD/MTCD and/or a biologically active dose (eg, recommended phase 2 dose [RP2D]) of the combination in specific tumor types.

[figure not shown]
The dose expansion part of the study (Part 2) will be opened once the MTD/MTCD/RP2D of the combination has been determined in Part 1.

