#### 4.2.1 Replacement of Subjects

Ineligible subjects (ie, subjects who were exposed to investigational product but post hoc were found to be ineligible) may be replaced. During Part 1, subjects who are not DLT-evaluable may be replaced (see Section 6.2.1 for a definition of DLT-evaluable). All available safety data for subjects who are not DLT evaluable will still be evaluated and considered in DLRT recommendations. Refer to Section 7.2.2 for information regarding replacement of subjects who receive AMG 994 in combination with AMG 404. Subjects who are withdrawn or removed from treatment or the study during Part 2 will not be replaced.

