A best overall response of SD requires an on-study imaging of SD or better no earlier than 7 weeks after cycle 1 day 1; otherwise the best overall response will be not evaluable (NE) unless PD is identified.

Evaluation of overall response details provided in protocol appendix 11.

Change from Baseline

Change from Baseline is the arithmetic difference between post-dose assessments and Baseline value.

Change (absolute) from Baseline = (Post-baseline Value – Baseline Value)

Change (percent) from Baseline = [(Post-baseline Value – Baseline Value)/Baseline Value] x 100

C_{max}

Maximum observed plasma drug concentration.

Dose Limiting Toxicity (DLT)

DLTs are the severe toxicities during the first cycle of cancer therapy. A Dose Limiting Toxicity (DLT) is defined as any AE (meeting the criteria listed in section 6.2.1.5 of protocol) occurring during the first treatment cycle of AMG 994 [REDACTED] where relationship to AMG 404 cannot be ruled out.

The DLT window (DLT-evaluable period) will be the first [REDACTED] of AMG 994 treatment (starting cycle 1, day 1). A subject is evaluable if subject experiences a DLT or completes [REDACTED] of treatment. DLT window will begin from Cycle 2 through study [REDACTED] [REDACTED] for combination of AMG 994 and AMG 404.

Duration of Response (DOR)

The duration of response is defined as time from first evidence of PR or CR to disease progression or death due to any cause. .

DOR will be calculated only for subjects who achieve a confirmed best overall response of PR or better.

DOR (in months) = (Earliest date of disease progression, death, censor - Date of first observation of PR or better + 1)/30.4

Dates of progression and censoring will be determined as described below in table 5.1.

End of Study (End of Trial)

The end of study date is defined as the date when the last subject across all sites is assessed or receives an intervention for evaluation in the study (e.g., last subject last visit), following the final protocol-specified visit (e.g. SFU) or any additional parts in the study (e.g., long-term follow-up, additional antibody testing) whichever is later.

End of Study (Individual Subject)

End of study for each subject is defined as the date the subject last completed a protocol-specified procedure. The date will be recorded on the End of Study CRF page.

End of Study (Primary Completion)

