9.6 Safety Analyses

9.6.1 Analyses of Primary Safety Endpoint(s)

Unless otherwise specified, statistical analyses on safety endpoints will be done using subjects from the safety analysis set, which includes subjects that are enrolled and received AMG 994 or AMG 404. The analysis of early DLTs will be conducted on the Early DLT Analysis Set and the analysis of cumulative DLTs will be conducted on the Cumulative DLT Analysis Set. Subject incidence of both early and cumulative DLT will be tabulated by planned dose level. A table of both early and cumulative DLTs will be provided. The probability of a subject having an early and cumulative DLT by dose level will be estimated using a 2-parameter BLRM model.

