9.6.2 Adverse Events

The Medical Dictionary for Regulatory Activities (MedDRA) version 23.0 or later will be used to code all adverse events to a system organ class and a preferred term. Where appropriate the tables will also be presented by worst grade.

Treatment-emergent adverse events will be summarized based on the number (%) of subjects experiencing events by MedDRA SOC and PT. The denominator for the percentage will be based on the number of subjects in the safety analysis set.

The subject incidence of adverse events will be summarized for

- TEAE
 - All treatment-emergent AEs
 - Grade 3 or higher treatment-emergent AEs
 - Treatment-emergent SAEs
 - Treatment-emergent AEs leading to interruption of investigational product
 - Treatment-emergent AEs leading to withdrawal of investigational product
 - Fatal treatment-emergent AEs
- Treatment-related AEs
 - All treatment-related AEs
 - Grade 3 or higher treatment-related AEs

- Treatment-related SAEs
- Treatment-related AEs leading to interruption of investigational product
- Treatment-related AEs leading to withdrawal of investigational product
- Fatal treatment-related AEs

The summaries that are displayed by SOC, PT and grade will be ordered by descending order of incidence of SOC, PT and grade within each SOC for the total group.

The above adverse event tables will not be created if two or fewer subjects experience the adverse event.

Dose Limiting Toxicities

The analysis of the probability of DLTs will include data from DLT-evaluable subjects

The primary analysis will only include DLTs that occur during the DLT evaluation period.

If DLTs occur outside the DLT evaluation period, a sensitivity analysis will be performed where DLTs occurring outside of the specified time interval are included. The number and percentage of subjects evaluated by tumor type and planned dose level.

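### In the sequential Part 1 cohorts, the Cumulative DLT set keeps every monotherapy DLT but drops DLT-free completers not evaluable on the combination, so cumulative DLT incidence is biased upward if leaving is unrelated to risk

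*SAP*

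**What the plan says.** Part 1 starts treatment in two ways (protocol 4.1). Sequential cohorts receive "1 cycle of AMG 994 monotherapy followed by combination of AMG 994 and AMG 404 from cycle 2 onwards". Concurrent cohorts have "AMG 994 and AMG 404 dosing starting on cycle 1 day 1".

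There are two DLT analysis sets. The Early set (SAP 6.3) holds subjects evaluable in the monotherapy window. The Cumulative set (SAP 6.4, with the same rule in protocol 9.3.1) holds subjects who "experience a DLT during monotherapy cohort or evaluable in combination therapy cohort". The DLT definition in SAP Section 5 gives the meaning of evaluable: "A subject is evaluable if subject experiences a DLT or completes" the window. The window length is blacked out and the table with the details is not visible.

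On analysis, SAP 9.6.1 tabulates early and cumulative DLT incidence by dose level and adds: "The probability of a subject having an early and cumulative DLT by dose level will be estimated using a 2-parameter BLRM model". SAP 9.6.2 adds: "The analysis of the probability of DLTs will include data from DLT-evaluable subjects". Protocol 4.1 says that the combination MTD/MTCD "will be determined using a Bayesian Logistics Regression Model (BLRM) design". Protocol 4.2.1 foresees non-evaluable subjects: "During Part 1, subjects who are not DLT-evaluable may be replaced".

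**The concern.** For a sequential subject, entry to the Cumulative set depends partly on the outcome being counted. A DLT in cycle 1 is enough. No DLT in cycle 1 is not enough, because the subject must also start the combination and become evaluable on it. Someone who completes monotherapy without a DLT and then leaves, for example through progression or withdrawal, counts as a non-event in the Early set and disappears from the Cumulative set. The numerator keeps all monotherapy DLTs while the denominator loses some monotherapy non-events.

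DLTs are a primary endpoint, so a tabulated primary result is affected. The only DLT sensitivity analysis in SAP 9.6.2 adds DLTs that fall outside the window. No planned analysis gives leavers credit in the cumulative figure for the monotherapy window they completed.

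**Working it through.** **The plan's own figures.** SAP 3.2 gives the chance of at least one DLT at true rates of 10% to 33%. From 1 − (1 − p)^n:
- n = 3: 1 − 0.90³ = 27.1% and 1 − 0.67³ = 69.9% (stated 27% to 70%).
- n = 6: 1 − 0.90⁶ = 46.9% and 1 − 0.67⁶ = 91.0% (stated 47% to 91%).

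These reproduce. They show the range of DLT rates the plan has in mind but say nothing about the bias.

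**Inputs for the bias, all assumed.**
- p1: DLT probability in the monotherapy window, 5% to 15%.
- p2: DLT probability in the combination window given no monotherapy DLT, 5% to 20%.
- d: share of DLT-free monotherapy subjects who never become evaluable on the combination, 10% to 50%. Leaving is taken as unrelated to DLT risk.

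**Formulas.**
- True cumulative rate: T = 1 − (1 − p1)(1 − p2).
- Expected rate in the SAP 6.4 set: E = [p1 + (1 − p1)(1 − d)p2] / [p1 + (1 − p1)(1 − d)].
- Difference: E − T = p1 · d · (1 − p1)(1 − p2) / [1 − d(1 − p1)]. This is zero if p1 = 0 or d = 0, and otherwise positive for p1 and p2 below 1.

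**One case in full.** With p1 = 10%, p2 = 15%, d = 30%: T = 1 − 0.90 × 0.85 = 23.5%. The DLT-free subjects who stay make up 0.90 × 0.70 = 0.63, so E = (0.10 + 0.63 × 0.15)/(0.10 + 0.63) = 0.1945/0.73 = 26.6%, an excess of 3.1 points. A simulation of 400,000 subjects gave 23.5% and 26.7%.

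| p1 | p2 | T | E, d = 10% | E, d = 20% | E, d = 30% | E, d = 50% |
|---|---|---|---|---|---|---|
| 5% | 15% | 19.25% | 19.7% | 20.2% | 20.9% | 23.1% |
| 10% | 10% | 19.0% | 19.9% | 21.0% | 22.3% | 26.4% |
| 10% | 15% | 23.5% | 24.3% | 25.4% | 26.6% | 30.5% |
| 15% | 10% | 23.5% | 24.8% | 26.3% | 28.1% | 33.5% |

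Over the whole grid the excess runs from 0.4 to 10.5 points. At p1 = 10% and d of 10% to 30% it is about 1 to 3 points.

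**In a group of six evaluable subjects.** For p1 = 10%, p2 = 15%, d = 30%, the chance of two or more DLTs, 1 − (1 − p)⁶ − 6p(1 − p)⁵, is 43.0% at p = 23.5% and 50.5% at p = 26.6%.

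**Replacement.** Replacements enter the set under the same rule, so the expected rate in the set is still E.

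**Counts.** Suppose 10 are treated, with 1 monotherapy DLT, 3 DLT-free leavers, and 6 evaluable on the combination with 1 DLT. The SAP set gives (1 + 1)/(1 + 6) = 28.6%. The stagewise estimate gives 1 − (9/10)(5/6) = 25.0%.

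**The case against.** **The MTCD.** A reader might infer that the BLRM curve comes out too steep and the MTCD too low. The documents do not support that. No visible text names the set that feeds the MTCD model, and much of the BLRM detail is blacked out. The formula for E describes the tabulated incidence; the BLRM posterior uses a prior and borrows across doses, and no BLRM was fitted here. What stands is narrower: of the two DLT sets, only the cumulative one contains combination-window events, so a link is plausible.

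**Reach.** Concurrent cohorts have no monotherapy stage, and Part 2 also gives both drugs from cycle 1 day 1 (protocol 4.1). The point does not extend to either.

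**Informative leaving.** Leavers might carry a higher combination DLT risk. In the worked case, the sign reverses only if their risk exceeds about 26.6%, against 15% in those who stay. That looks unlikely, since an event requiring permanent discontinuation of AMG 994 is itself a DLT (protocol 6.2.1), so DLT-free leavers should mostly leave for other reasons. But the stagewise estimate is not unbiased without this assumption. With leaver risk x, the truth is 0.1945 + 0.27x. It lies midway between 23.5% and 26.6% at x of about 21%; above that, the current set is nearer the truth.

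**Mitigation.** The Early set counts the leavers correctly for monotherapy. The dose level review team considers data from non-evaluable subjects, and the BLRM does not decide alone. The error also errs on the cautious side in a first-in-human trial. All of this lowers the stakes, but none of it corrects the reported cumulative incidence.

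**Conclusion.** The point holds for the sequential Part 1 cohorts. Given some monotherapy DLTs, some loss of DLT-free subjects, and leaving unrelated to DLT risk, cumulative DLT incidence in the SAP 6.4 set overstates the true rate. The size cannot be fixed from the documents. It is about 1 to 3 points at 10% monotherapy DLTs and 10% to 30% loss, 4.6 points at p1 = 15%, p2 = 10% and 30% loss (28.1% against 23.5%), and zero if either ingredient is absent. The direction is conservative. An effect on the selected combination dose remains an inference. This justifies adding an estimate, not replacing the dose-finding model.

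**What to change.** In SAP 6.4 and 9.6.1, with matching text in protocol 9.3.1 and 9.4.2.3.1 so that the documents stay aligned, add for the sequential cohorts the stagewise cumulative estimate 1 − (1 − p_early)(1 − p_comb). Take p_early from the Early DLT set and p_comb from combination-evaluable subjects without an early DLT. Report it by dose level beside the current set-based incidence, and show both at dose level reviews. Leave the 2-parameter BLRM unchanged: a two-factor likelihood would need a second prior and is a separate, debatable step.

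The cost is wording in four places and a little extra analysis on data already collected. An interval method must be named, because the exact binomial interval in SAP 9.1 does not apply to a product. The estimate still assumes non-informative leaving, and it keeps the usual asymmetry within each window, where a DLT makes a subject evaluable but a DLT-free subject must complete.
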